2.7.3.3 Objective evaluation of antidepressant effectiveness

The main clinical outcome is relapse of depression, defined using the MADRS and SCID depression module. Patients with a 2 point or greater increase from their average baseline open-label lead-in phase MADRS score, and/or MADRS score of 15 or greater, will have the SCID depression module conducted. If the SCID reveals current MDD, they will be considered to have relapsed. Physician adjudication (by study Psychiatrist, who is blinded to randomization assignment) will be utilized as well.² An appropriate generalized linear model with a binomial link function will be used. Relapse of depression will also be considered an end-point in the study.

Subjects suffering a relapse will be removed from the study and will return to their pre-study bupropion product. Subjects will be advised to contact their treating physician for follow-up. Data and specimens collected for these subjects will be included in the analysis.

The secondary clinical outcomes are symptomatic change in depression (MADRS scores) and side effects (Antidepressant Side Effect Checklist scores) determined at the every 3-week interviews. Repeated measures ANOVA analogues of the models described above will be used for each of these analyses. Analysis will test for any systematic effects of differences between patient's symptom/side effect levels with Wellbutrin XL and each generic preparation.

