2.5 Patient Selection

An estimated 75 subjects with MDD in partial or full remission who are currently taking bupropion 300mg XL (branded or generic) will be enrolled. The target enrollment is 60 evaluable subjects. A 25% drop-out rate is conservatively assumed. Subjects must be on stable therapy (minimum of 4 months on bupropion 300mg XL). Subjects will be recruited from the Washington University patient population, by referrals from community physicians, and by public advertisements. Potential subjects will also be contacted by the pharmacy benefit manager Express Scripts, given a brief description of the study, and invited to contact the investigators for further information and potential recruitment/enrollment. The study will be posted on clinicaltrials.gov, once reviewed and approved by the Research Involving Human Subjects Committee (RIHSC), the FDA's Institutional Review Boards (IRB). Subjects will be screened with the Structured Clinical Interview for DSM Axis I Disorders (SCID) to determine eligibility. SCID assesses current and lifetime depression, as well as other psychiatric disorders, and is used to clarify psychiatric inclusion and exclusion criteria. Participants must have MDD which is in partial or full remission. All risks and benefits will be explained, and subjects will sign an informed consent form. After enrollment a blood sample will be obtained, coded for deidentification (see 3.3.4 below) and stored at -80°C in the PIs lab for later DNA analysis. DNA is stored until all reports and manuscripts are completed and accepted.

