2.6.5 Randomized Study Period

Subjects will take each 300mg bupropion XL product for 6 weeks, and then be switched to another product without washout, according to their randomization schedule. During the 2nd-3rd week on each product, subjects will visit the study clinic for a bupropion pharmacokinetic session, an objective assessment of depression and side effects, and to receive another 3 week supply of study drug. During the 6th week on each product, subjects will again visit the study clinic for objective assessments of depression and side effects. Subjects will then be switched to their next scheduled drug product, and the sequence repeated for the four study drugs. Each subject will therefore be studied for four 6-week study drug epochs. Subjects will not be informed when they are being switched, in order to minimize bias. A Medication Event Monitoring System, (MEMS 6 TrackCap, or equivalent) will be used to assess compliance and compile drug dosing histories for the quantitative analysis of adherence during each subject's 28 week study period.

The rationale for the timing of the pharmacokinetic assessments is as follows: Subjects must be at steady-state on their new bupropion product. Steady-state bupropion concentrations have been reported to occur by 8d for all formulations. ¹⁸ Nevertheless, to ensure that metabolites disposition is also at steady-state, and metabolite elimination is known to be somewhat slower than parent, at least 10d will be allowed before assessing pharmacokinetics. Assessment should not wait too long, however, in case a patient reports loss of effectiveness or side effects after starting a new bupropion product, causing a product switch or other intervention, and this risk increases with time. Therefore the 10-20 day window will be targeted for the bupropion pharmacokinetic session for each product.

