2.7.4 Sample Size Justification

Calculations for sample size and power of the proposed studies are based on information from the confidence intervals for the ratio of the pharmacokinetic parameters for the generic (Budeprion XL) to the innovator (Wellbutrin XL) which was recently reported by the FDA in their evaluation of Budeprion XL.⁵¹

SAS 9.3's Proc Power was used to conduct the correct power analysis for the two one-sided tests (TOST) approach per the FDA guidance on bioequivalence. Using a 90% confidence interval and ratios needing to be between 0.80 and 1.25, the power for sample sizes ranging from a conservative estimate of 60 to the recruitment goal of 75 was computed. If the comparators are indeed bioequivalent (ratio=1.0) then the study power would be >0.999 for a pharmacokinetic parameter such as AUC and 0.98 for a more variable parameter such as C_{max} . If the generic is 10% under (or over), e.g. ratio=0.90,

then for AUC the power would be 0.78=0.83 to declare a significant difference between the compounds at an alpha of .05 even if the CI for the ration was still contained within the 0.80-1.25 bounds.

Ver 1.02

The study is also powered in order to have a reasonable power of detecting clinical differences between compounds. If one of the generics is non-equivalent with respect to symptom and it is assumed that 25% suffer a relapse on this generic versus 5% for Wellbutrin or other (equivalent) forms, then using a McNemar's test for equality of proportions, a sample size of 60 and a 1-tailed alpha of 0.05, the power will be about 0.83. For continuous variables, there will be 0.80 power to detect a standardized difference of 0.37 (low-medium effect size).

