3. MANAGEMENT OF INTERCURRENT EVENTS

There is a naturalistic recurrence (relapse) rate of depression of about 5% yearly for patients who maintain adherence with a stable dose of medication to which they initially responded. Thus, even if all forms of bupropion XL are clinically equivalent, about 3-4 participants may be expected to suffer a relapse during the trial. Relapse of depression is considered an end-point in the study: patients who have suffered a relapse will be removed from the study and will return to their prestudy medication formulation. Study staff will ensure that relapsed study subjects restart their medication and receive timely follow-up with their treating physician or other appropriate mental health professional. In the case that relapse of depression is associated with the emergence of suicidal ideation, this could include hospitalization. Patients who prematurely discontinue or are non-adherent to study medication will be removed from the study. The most likely outcome is for the patient to return to their pre-study medication formulation. Other risks are those that would follow a breach of confidentiality and the disclosure of clinical information. In addition, it is recognized that depressed individuals, especially those with chronic illness and disability, can easily feel overwhelmed or fatigued by what would be minimally demanding tasks for others, and, therefore, this discomfort is included in the potential risks. The instruments to be used in this study have been used by the investigators in other studies of older depressed adults (including older frail adults). There are very few older adults who are unable to tolerate the length of the questionnaires.

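### The relapse model in 2.7.3.3 names no test and makes no provision for a product with zero relapses, which section 3's own event count makes likely

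*Combined protocol and SAP*

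**What the plan says.** Section 2.7.3.3 calls relapse the main clinical outcome. Its analysis is "An appropriate generalized linear model with a binomial link function will be used". Binomial is a distribution family and not a link, so the link is left open. So are the test, the interval method, the handling of repeated phases, and what happens if a product has no relapses. The same section says "Subjects suffering a relapse will be removed from the study", so each subject contributes at most one relapse and is not observed on later products.

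Two baseline relapse rates appear:

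- Section 3: "There is a naturalistic recurrence (relapse) rate of depression of about 5% yearly for patients who maintain adherence", from which the plan concludes that, with all products equivalent, "about 3-4 participants may be expected to suffer a relapse during the trial".
- Section 2.7.4: "it is assumed that 25% suffer a relapse on this generic versus 5% for Wellbutrin or other (equivalent) forms". This treats 5% as the risk on each product. The power statement there ("a sample size of 60 and a 1-tailed alpha of 0.05, the power will be about 0.83") is for McNemar's test and not for the model in 2.7.3.3.

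Exposure per product is short: "Subjects will take each 300mg bupropion XL product for 6 weeks" (2.6.5). The target is 60 evaluable subjects (2.5).

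**The concern.** With very few relapses spread over four products, some product is likely to have none. In a logistic model with product as a factor, a product with zero events pushes its maximum-likelihood log-odds to minus infinity. Any odds ratio against it is then infinite, or undefined if both products have none. The Wald standard error diverges with the estimate, so the Wald p-value goes to about 1 even when the other product has many relapses.

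Two things are at stake. If the products are alike, the brand-generic odds ratios may not be reportable. If one generic is worse and the baseline is as low as section 3 implies, a Wald test could report no difference where the raw counts show a large one. Because the text leaves the test open, the choice would be made after the counts are seen, when it can decide the conclusion.

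**Working it through.** **1. The plan's own count.** 60 × 5% = 3.0 and 75 × 5% = 3.75, which reproduces section 3's 3-4. The match uses a full year of risk. Over 28 weeks it would be 60 × 5% × 28/52 = 1.6 to 75 × 5% × 28/52 = 2.0.

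**2. How often a brand-generic pair includes a zero.** Assume equal risk on each product.

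- *Total of T relapses over four products.* P(at least one zero in a given pair) = 2(3/4)^T − (1/2)^T, and P(both zero) = (1/2)^T. For T = 3: 0.844 − 0.125 = 72%, of which 12.5% are both zero and 59% exactly one. For T = 4: 0.633 − 0.0625 = 57%, of which 6% are both zero and 51% exactly one. At least one of the four products has zero in 100% (T = 3) or 91% (T = 4).
- *5% a year pro-rated to six weeks.* 5% × 6/52 = 0.58% per phase, and 60 × 0.58% = 0.35 relapses per product. P(zero on one product) = (1 − 0.0058)^60 = 71%. P(at least one zero in a pair) = 1 − (1 − 0.707)² = 91%: both zero in 50%, exactly one in 42% (rounded).
- *5% per product, as in 2.7.4.* 60 × 5% = 3 per product, and P(zero) = 0.95^60 = 4.6%. P(at least one zero in a pair) = 1 − 0.954² = 9%. With removal at relapse the whole-trial total is 60 × (1 − 0.95⁴) = 11, against 3-4 in section 3, so the two sections do not describe the same baseline.

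**3. What the fit does with a zero.** Two-sided p-values:

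| Brand | Generic | Wald | Likelihood ratio | Firth | Fisher |
|---|---|---|---|---|---|
| 0/60 | 5/60 | 0.999 | 0.0075 | 0.024 | 0.057 |
| 0/60 | 6/60 | 0.999 | 0.003 | 0.011 | 0.027 |
| 0/60 | 15/60 | 0.999 | <0.0001 | <0.0001 | <0.0001 |

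The maximum-likelihood standard error is about 17,000 in each row. The Firth odds ratio stays finite (14.4 for 6/60 against 0/60). In the 5/60 row the tests fall on both sides of 0.05.

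**4. Power, one generic at 25%.** Simulated trials of 60 subjects, removal at relapse, brand against that generic, two-sided 0.05. Simulation error is about one to two points.

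| Brand risk per phase | Brand has zero | Wald | Firth | Likelihood ratio |
|---|---|---|---|---|
| 0.59% (5% a year, as 1 − 0.95^(6/52)) | 73% | 26% | 99.7% | 99.8% |
| 1-1.25% | – | 40-44% | about 99% | over 99% |
| 5% (2.7.4) | 8% | 76% | 86% | 88% |

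Over four phases and 60 subjects, 1% is 2.4 relapses under equivalence and 1.25% is 3.0, so this row sits at or just below the low end of section 3's range. At 3.5 relapses (1.46% per phase), without removal, Wald power is 57%, against 99.5% for likelihood ratio and 98% for Fisher.

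**5. False positives with all products equal.** At nominal 5%, the likelihood-ratio test rejects in under 1% of trials at the pro-rated rate and in up to about 9% at 5% per product. Firth stays at or below 3%.

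**The case against.** The strongest reply is that the text asks for an appropriate model and names neither maximum likelihood nor Wald. Bias-reduced fitting or likelihood-ratio inference would be compatible with it. That stands: the loss of power belongs to one test statistic, and the plan does not commit to it. It does not close the gap. No choice is fixed in advance, the likelihood-ratio test can exceed its nominal level, and the ordinary odds ratio is not finite with a zero whichever test is used.

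A reader might infer that the planned analysis would usually miss the very difference the trial is sized to find. The documents do not support that. Section 2.7.4 sizes on 25% against 5% per product, where brand has no relapses in only about 8% of trials. Wald power there is about 76% two-sided, and about 84% at the plan's one-tailed 0.05, close to the stated 0.83. The 26% figure arises only when 2.7.4's 25% is paired with section 3's yearly rate pro-rated to six weeks, a pairing the plan does not make.

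Two further points also stand. Relapse is listed among the secondary endpoints in 2.7.1, and depression and side-effect scores are analysed separately as continuous measures. And no method recovers much information from one or two events: a Firth or exact interval will be very wide. Per-product proportions can be reported under the present wording.

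**Conclusion.** The point holds as a gap in the specification with a real numerical consequence at section 3's relapse count. At 3-4 relapses in the trial, about 57-72% of brand-generic comparisons include a zero-relapse product, and about 91% do at the pro-rated rate. In those comparisons an ordinary fit has no finite odds ratio. If a Wald test were used and one generic were at 25%, power would be about 26% at the pro-rated brand rate and 40-44% at 1-1.25% per phase, where the alternatives reach about 99%. In 2.7.4's scenario the cost is about ten points of power (76% against 86% for Firth). It should not be read as a general failure of the planned model or as a flaw in the McNemar power figure, which is a separate calculation and not relied on here.

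Assumptions: equal relapse risk per phase for equivalent products, 60 subjects starting, balanced orders, no drop-out other than relapse, and a marginal product comparison at two-sided 0.05. Removing relapsers changes the zero probabilities by only a few points.

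**What to change.** In 2.7.3.3, replace the model sentence with: relapse will be analysed by Firth-penalised logistic regression on product-phases at risk, each subject contributing phases up to and including the phase of relapse, with product as a factor and with tests and intervals from the profile penalised likelihood. Add that each product's relapse proportion will be reported with an exact (Clopper-Pearson) interval. State whether the test is one- or two-sided.

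Reconcile the baseline relapse rate in 2.7.4 (5% on each product) with that in section 3 (5% a year, 3-4 relapses in the trial), so that the expected number of events is stated once.

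The cost is SAP wording only, with no change to conduct or sample size. The downsides are slight shrinkage of the odds ratio and intervals that will still be wide with so few events.

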2.7.4 Sample Size Justification

Calculations for sample size and power of the proposed studies are based on information from the confidence intervals for the ratio of the pharmacokinetic parameters for the generic (Budeprion XL) to the innovator (Wellbutrin XL) which was recently reported by the FDA in their evaluation of Budeprion XL.⁵¹

SAS 9.3's Proc Power was used to conduct the correct power analysis for the two one-sided tests (TOST) approach per the FDA guidance on bioequivalence. Using a 90% confidence interval and ratios needing to be between 0.80 and 1.25, the power for sample sizes ranging from a conservative estimate of 60 to the recruitment goal of 75 was computed. If the comparators are indeed bioequivalent (ratio=1.0) then the study power would be >0.999 for a pharmacokinetic parameter such as AUC and 0.98 for a more variable parameter such as C_{max} . If the generic is 10% under (or over), e.g. ratio=0.90,

then for AUC the power would be 0.78=0.83 to declare a significant difference between the compounds at an alpha of .05 even if the CI for the ration was still contained within the 0.80-1.25 bounds.

Ver 1.02

The study is also powered in order to have a reasonable power of detecting clinical differences between compounds. If one of the generics is non-equivalent with respect to symptom and it is assumed that 25% suffer a relapse on this generic versus 5% for Wellbutrin or other (equivalent) forms, then using a McNemar's test for equality of proportions, a sample size of 60 and a 1-tailed alpha of 0.05, the power will be about 0.83. For continuous variables, there will be 0.80 power to detect a standardized difference of 0.37 (low-medium effect size).

3. MANAGEMENT OF INTERCURRENT EVENTS

There is a naturalistic recurrence (relapse) rate of depression of about 5% yearly for patients who maintain adherence with a stable dose of medication to which they initially responded. Thus, even if all forms of bupropion XL are clinically equivalent, about 3-4 participants may be expected to suffer a relapse during the trial. Relapse of depression is considered an end-point in the study: patients who have suffered a relapse will be removed from the study and will return to their prestudy medication formulation. Study staff will ensure that relapsed study subjects restart their medication and receive timely follow-up with their treating physician or other appropriate mental health professional. In the case that relapse of depression is associated with the emergence of suicidal ideation, this could include hospitalization. Patients who prematurely discontinue or are non-adherent to study medication will be removed from the study. The most likely outcome is for the patient to return to their pre-study medication formulation. Other risks are those that would follow a breach of confidentiality and the disclosure of clinical information. In addition, it is recognized that depressed individuals, especially those with chronic illness and disability, can easily feel overwhelmed or fatigued by what would be minimally demanding tasks for others, and, therefore, this discomfort is included in the potential risks. The instruments to be used in this study have been used by the investigators in other studies of older depressed adults (including older frail adults). There are very few older adults who are unable to tolerate the length of the questionnaires.

3.1 Adverse Events

Significant drug-related adverse events are expected to be uncommon, as participants in this study are being continued on bupropion at a dose that they are currently tolerating well (study inclusion criterion). Bupropion, tends to produce side effects early in treatment, so late-appearing side effects are unlikely, especially if bioequivalence is observed). Nevertheless, there is a rare risk for new, significant side effects, even with our procedures to select participants with low likelihood of these. The investigative team will closely monitor subjects for adverse events. Adverse events will be reported to the RIHSC and to the Washington University IRB according to applicable guidelines. Adverse events are followed until satisfactory resolution, as determined by the investigators. The description of the adverse experience will include the description, date and time of onset, duration, intensity, etiology, relationship to the study drug (none, unlikely, possible, probable, highly probable), any treatment required, and any follow-up and/or treatment required.

3.2 Premature Discontinuation

If a subject withdraws or drops out from the study, or is withdrawn by the investigators, they will be replaced, to provide the required number of subjects. Subjects will be withdrawn if the investigator decides that discontinuation is in the best interest of the subject, or the subject requests withdrawal from the study. Subjects' participation can be terminated by the investigator without regard to the subject's consent. Randomization of replacements will be as follows:

- 1. Subjects withdrawn or dropping out prior to randomization (before or during the lead-in) will simply be replaced in that former subject's randomization, and receive that subject's order of drug products
- 2. Subjects withdrawn or dropping out after randomization, while receiving the study drugs, will be replaced using the next scheduled randomization sequence.

3.3 Potential Risks

3.3.1 Potential risks from bupropion

Adverse effects from bupropion: Bupropion is a widely used and efficacious antidepressant also used for smoking cessation. All enrolled subjects will currently be taking this drug under the management of their treating physician at the time of enrollment. Bupropion is generally well-tolerated. In patients taking it chronically, it may cause agitation, anxiety or insomnia. A rare effect of bupropion is seizures, which are partially dose-related, and the risk is also increased in

patients with a history of seizure disorders or other predisposing factors. The incidence of seizure in patients receiving bupropion at doses <450mg daily is about 0.1-0.4%, similar to other antidepressants. The potential risks and side effects from versions of bupropion HCl manufactured by Valeant Intl (Wellbutrin), Anchen/Par Pharmaceuticals, Watson, and Mylan will be explored from this proposed research to determine if patients can perceive differences in release patterns, clinical effectiveness, and adverse events between drug preparations.

3.3.2 Potential Risks from Drug Cross-Over

The intent of the study is to determine whether the forms of bupropion 300mg XL are bio- and clinically-equivalent; therefore, there is some chance that some of the forms are not equivalent and patients will be switched to a form that is either ineffective or causes side effects. The risk of this is unknown. However, these risks are not unlike typical clinical care in which patients may be switched between generics for reasons of cost or availability at any refilling of medications.

3.3.3 Potential Risks from Discomfort Related to Interviews And Questionnaires

With respect to minimizing any discomfort that may result from the interview, raters have been or will be selected on the basis of personal attributes and interpersonal skills as well as substantive knowledge. They will be further trained and periodically observed to ensure that they are respectful and sensitive to the needs and feelings of the subjects. Furthermore, they are trained to recognize signs of significant stress or irritability and will be instructed that they should gently terminate the interview whenever distress is observed.

